## 3 INVESTIGATIONAL PLAN

### 3.1 OVERALL STUDY DESIGN AND PLAN

This single-group, small-scale, open-label study (N= 25 to 50) will evaluate the impact of combination zonisamide and bupropion on the process of switching from combustible cigarettes (CC) to an e-cigarette. There will be a data collection period of at least five days to obtain baseline data on use of combustible cigarettes. Participants enrolled in the study will receive a G6 e-cigarette at V2 for *ad libitum* use. After the first week of e-cigarette use, (at V3) participants will be given zonisamide (100 mg/daily) and will begin extended-release bupropion dosing (150 mg each morning days 1-3, then 300 mg/daily) in addition to continued use of the G6. At each visit, participants will receive enough zonisamide, bupropion, and Halo G6 cartomizers to last until their next study visit. Halo G6 and combination zonisamide and bupropion use will continue until the participant returns for the End-of-Study visit (V7).

[figure not shown]

Figure 1 - Overall Study Design

The outcome of the combination zonisamide and bupropion on the process of switching from combustible cigarettes (CC) to an e-cigarette will be compared to the following benchmarks. Initial results will fall into one of the following three categories:

**3.1.1 Complete switching rate of 64%**

If this study achieves at least a 64% (16/25) switching rate to Halo G6 for the first 25 smokers tested at V7, it will be viewed as having considerable promise, and will immediately be advanced to larger-scale (~N=200) randomized controlled clinical trials (RCTs) to provide a rigorous evaluation of its efficacy and effectiveness in helping smokers switch to e-cigarettes. Future trials will be submitted to the Institutional Review Board (IRB) as new protocols.

[figure not shown]
**3.1.2 Complete switching rate of 52% to 60%**

If this study achieves switching to Halo G6 in 52%-60% (13/25 to 15/25) of the first 25 smokers tested at V7, then an additional sample of 25 smokers will be enrolled (total N=50) to obtain a more precise estimate of the switching rate. If, cumulatively, complete switching to G6 is achieved in at least 56% (28/50) at V7, the use of combination zonisamide and bupropion as an aid to switching will then be advanced to larger RCTs.

**3.1.3 Switching Thresholds Not Achieved**

If either of the above switching rate thresholds is not met in the first 25-50 smokers tested, the use of combination zonisamide and bupropion as an aid to switching will be considered unpromising, and further participants will not be enrolled.

In choosing these thresholds, Monte Carlo simulations were conducted to determine the significance thresholds for both the N=25 and N=50 one-tailed binomial tests so that the overall false positive (Type I error) rate across all tests would be approximately 10%. Conversely, the overall false negative (Type II error) rate, whereby a promising procedure is discarded prematurely, would be approximately 20%. The diagram below depicts the stepwise evaluation algorithm.

**3.2 STUDY PROCEDURES**

At each session, expired air CO will be measured along with blood pressure, heart rate, respiratory rate and body weight. Participants will also complete questionnaires rating participative effects of smoking and e-cigarette use. Participants will be given enough cartomizers and study drugs to last until their next scheduled session, along with an extra 4 days' worth to allow for flexibility in case sessions need to be rescheduled. E-cigarette usage and study drug compliance will be tracked not only by self-reported number of occasions used, but also by cartomizer counts (used or unused) and returned study drugs.

### 3.3 POINT OF ENROLLMENT

Participants will be enrolled after all safety laboratory results have been received and reviewed by the medical staff (MD or PA). The Halo G6 and the cartomizers will be dispensed starting at V2, and at each subsequent visit until the End-Of-Study. Study drugs will be dispensed starting at V3, and at each subsequent visit until the End-Of-Study.

### 3.4 STUDY AND SESSION DURATIONS

The total duration for a participant will be approximately 14-16 weeks. The Screening Session (Visit 1) will last approximately 2 ½ to 3 hours. The other study sessions will last approximately one hour.

## 4 PARTICIPANT INVOLVEMENT

---

### 4.1 SELECTION OF STUDY POPULATION

Healthy, cigarette smoking adults, age 21-65 years, with no restriction on gender, race and ethnicities, or social-economic status, who have smoked an average of at least 10 commercially available cigarettes per day for the last 12 months will be screened for enrollment in this study.

The study will screen and enroll at both Rose Research Center locations, located in Raleigh and Charlotte, North Carolina.

#### 4.1.1 Inclusion Criteria

Each participant must meet all the following inclusion criteria before enrollment:

Inclusion Criteria
1. Has signed the ICF and is able to read and understand the information provided in the ICF.
2. Is 21 to 65 years of age (inclusive) at screening.
3. Smokes at least 10 commercially available cigarettes per day (no brand restrictions), for the last 12 months.
4. Has an expired air CO reading of at least 10 ppm at screening.
5. Interested in switching to an electronic cigarette.
6. Willing and able to comply with the requirements of the study.
7. Owns a smart phone with text message and data capabilities compatible with necessary surveys.

#### 4.1.2 Exclusion Criteria

Potential participants who show or report indications of or self-report a diagnosis of conditions listed below may be excluded from the study. If the study physician (or designee) determines through the course of pre-screening, or a physical screen, medical history, physical findings, current medications, ECG, or laboratory findings suggests one of the conditions listed below, or findings reveal other information that may potentially jeopardize the participants' safe participation, then they may be excluded. For medical conditions that do not appear below,

the participant may be enrolled if the study physician (or designee) does not feel that the medical condition would jeopardize safe study participation or data validity.

Exclusion Criteria
1. Is unhealthy or cannot participate in the study for any reason (e.g., medical, psychiatric, and/or social reason) as judged by the Investigator or designated medical staff based on all available assessments from the screening period (e.g., safety laboratory, vital signs, physical examination, ECG, concomitant medications and medical history).
2. PHQ-9 score greater than 9, or a score greater than 0 on item #9 (“Thoughts that you would be better off dead, or of hurting yourself in some way”) at screening.
3. Planned use of an FDA-approved smoking cessation product during the study.
4. High blood pressure (systolic > 150 mmHg or diastolic >95 mmHg) at screening.
5. Body mass index (BMI) less than 15.0 kg/m  or greater than 40.0 kg/m  .
6. Coronary heart disease, structural cardiac disease (including, but not limited to valvular heart disease or cardiac murmurs), cardiac dysrhythmias, syncope, cardiac chest pain, or history of heart attack or heart failure.
7. Has received psychotherapy or behavioral treatments potentially impacting symptoms of depression, anxiety, or nicotine withdrawal within 30 days of screening, or during the study.
8. Taking antidepressants, psychoactive medications (e.g. antipsychotics, benzodiazepines, hypnotics) or medications that prolong QT c .
9. Use of any of these products in the past 30 days: 
 
a. Illegal drugs (or if the urine drug screen is positive for cocaine, THC, amphetamines, methamphetamines, or opiates);
 
b. Experimental (investigational) drugs that are unknown to participant;
 
c. Chronic opiate use.
 

10. Use of smokeless tobacco (chewing tobacco, snuff), cigars (except for “Black & Mild” cigars or Cigarillos), pipes, hookah, e-cigarettes, nicotine replacement therapy or other smoking cessation treatments within 14 days of screening.
11. Pregnant or nursing (by self-report) or has a positive pregnancy test.
12. Enrollment requirements met.

#### 4.1.3 Women of Childbearing Potential

Pregnant or breastfeeding women will be excluded from the study. All females will undergo a serum pregnancy test at screening (Visit 1) and a urine pregnancy test at each subsequent visit. Heterosexually active females of childbearing potential (not post-menopausal) must agree to use medically acceptable contraceptives during the study. Medically acceptable contraceptives include: (1) surgical sterilization (such as a tubal ligation, hysterectomy, or Essure), (2) approved hormonal contraceptives (such as birth control pills, patches, implants or injections), (3) barrier methods (such as a condom or diaphragm) used with a spermicide, or (4) an intrauterine device (IUD). Contraceptive measures such as Plan B™, sold for emergency use after unprotected sex, are not

acceptable methods for routine use. Female participants will be encouraged in the consent form to notify study staff if they believe a change in their pregnancy status has occurred during the trial.

Post-menopause is defined as the time after which a woman has experienced 12 consecutive months of amenorrhea (lack of menstruation).

## 4.2 RECRUITMENT STRATEGIES

Participants will be selected through IRB approved generic recruitment advertisements which are specifically designed to recruit participants into the volunteer database for future smoking and tobacco use related research at the Rose Research Center. For this database, many of the participants have provided basic smoking history data along with demographic information, which will allow selection of potentially interested participants.

Participants who call in will be screened into the volunteer database, and if they pre-qualify, will be offered the option to prescreen for this protocol.

Participants will be contacted only with IRB approved appropriate materials and information submitted along with this protocol. These documents will include a brief description of the study and information on how to prescreen for participation. Participants will be contacted by phone, email and text message prompting interested participants to prescreen through an electronic screen form.

### 4.2.1 Pre-Screening

Pre-screening will be completed prior to V1 for all participants. Participants will be provided with a set of IRB approved questions directly related to the inclusion and exclusion criteria. Based upon the outcome of these questions, potential participants may be scheduled for a screening visit (V1).

## 4.3 PARTICIPANT RETENTION IN THE STUDY

All candidates who schedule a screening visit (V1) will receive a series of email, text, and telephone reminders; participants are also permitted through these communications to confirm, cancel, or reschedule all their appointments.

## 4.4 DISCONTINUATION OF PARTICIPANTS FROM STUDY

Discontinued participants will include both participants who withdraw from the study (participant's decision) or participants who are discontinued from the study (following Investigator's decision). A participant can only be discontinued from the study after enrollment. Participants that are not enrolled are considered screen failures.

Participants will be informed that they are free to withdraw from the study at any time. Participants should be questioned for the reason of premature withdrawal from the study, although they are not obliged to disclose it.

Participants discontinued from the study cannot re-enter the study.

### 4.4.1 Participants will be discontinued from the study for any of the following reasons:

- Withdrawal of informed consent.
- Any adverse effect or condition that would jeopardize continued safe study participation.
- Pregnancy test is positive.

- Discontinuation is considered to be in the best interest for the participant or for other participants participating in the study, as judged by the Investigator or designee.

#### 4.4.2 Participants may be discontinued from the study for any of the following reasons based on the judgment of the Investigator:

- No-show to appointments and unable to reschedule within the visit window.
- The misuse or abuse of study related equipment.
- Potential loss of the participant's data validity.
- Unwilling or unable to comply with study procedures.
- Enrollment discontinuation.

### 4.5 LOST TO FOLLOW-UP

For participants lost to follow-up, a reasonable number of attempts to contact the participant (including written correspondence and/or phone calls) will be made and documented in the source documents. The date of the last contact (e.g. last visit, last phone call) will be recorded in the source document. When the PI (or designee) declares a participant is lost to follow-up, the lost to follow-up date will be recorded and will correspond to the date of the End of Study (EOS) of the participant.

### 4.6 VIOLATION OF INCLUSION/EXCLUSION CRITERIA

Participants who, after signing the ICF, do not meet the inclusion and exclusion criteria will not be enrolled in the study and will be considered screen failures. Re-screening for the study is not permitted.

### 4.7 PARTICIPANT COMPENSATION

There will be a payment of \$25 for the Screening Session (V1) and \$75 at the completion of each study session V2 through V7. Participants will also receive an additional payment of \$5/day for responding to daily text messages during the 13-week product use period. If participants provide a CO reading at the six-month follow-up, they will receive an additional \$25.

If participants are asked by study staff to return to the center to complete or redo parts of the screening in situations of equipment malfunctions or other circumstances that are beyond the participants' control, participants may be reimbursed for mileage.

Participants who decide to withdraw from the study will be paid for the part of the study they have completed.

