### 2.2 POINT ABSTINENCE (FROM CC) AT SIX MONTHS POST SWITCH

A secondary outcome will be 7-day point abstinence at 6 months post-switch, for participants who are smoking abstinent during weeks 8-11 post-quit, as defined above in Section 2.1. This will be assessed by self-report utilizing an automated SMS messaging system.

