### **8.4 6-MONTH FOLLOW UP**

Participants who complete the study will be contacted six months after the switch day utilizing an automated SMS messaging system, to ascertain their current smoking status and use of e-cigarettes. If a participant self-reports current abstinence from smoking they will be asked to return to the office for collection of an expired air CO for verification.

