## 8.6 SMS MESSAGING

8.6.1 Daily SMS Message (after screening, prior to V2) – Participants will receive a text with a link to a survey to access the following:

- Have you smoked any combustible cigarettes today?
  - If yes, how many cigarettes did you smoke?
  - What was your favorite cigarette of the day?  
1-First one, 2-One immediately after a meal, 3-Any other cigarette

8.6.2 Daily SMS Message (From Visit 2) -- Participants will receive a text with a link to a survey to assess the following:

- Have you smoked any combustible cigarettes today?
  - If yes, how many cigarettes did you smoke?
  - Which cigarette did you smoke today? (If only 1 cigarette is reported)  
1-First one of the day, 2-One immediately after a meal, 3-Any other cigarette
  - What was your favorite cigarette of the day? (Of more than 1 cigarette is reported)  
1-First one, 2-One immediately after a meal, 3-Any other cigarette
- Have you used your e-cigarette today?
  - If yes, how many times did you use your e-cigarette today?
- Did you take your study drugs this morning? (After Visit 3)

8.6.3 6-Month follow up SMS Message -- Participants will receive a text with a link to a survey to assess the following:

- Have you smoked a combustible cigarette since your last visit?
  - If yes, are you still smoking combustible cigarettes right now?
  - How many combustible cigarettes do you smoke per day on average?
- Have you used an e-cigarette since your last visit?
  - If yes, are you still using an e-cigarette?
  - How often do you use an e-cigarette?
- Have you used any other nicotine containing products (other than e-cigarettes) since you last visit?

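### At month 6 the text reply is unpaid and the only payment is reachable solely by participants who report abstinence, which risks an upward bias in the secondary 6-month outcome

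*Combined protocol and SAP*

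**What the plan says.** Four places in the combined protocol and SAP have to be read together.

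- **Section 4.7 (compensation), text replies.** Participants earn 5 dollars a day "for responding to daily text messages during the 13-week product use period". No payment is given for answering the month-6 text.
- **Section 4.7, month 6.** "If participants provide a CO reading at the six-month follow-up, they will receive an additional" 25 dollars. The payment is for providing a reading, and no CO value is required.
- **Section 8.4 (6-month follow-up).** "Participants who complete the study will be contacted six months after the switch day utilizing an automated SMS messaging system". Then: "If a participant self-reports current abstinence from smoking they will be asked to return to the office for collection of an expired air CO". No other route to a month-6 reading is described.
- **Section 2.2 (6-month outcome).** "A secondary outcome will be 7-day point abstinence at 6 months post-switch, for participants who are smoking abstinent during weeks 8-11 post-quit". On the method: "This will be assessed by self-report utilizing an automated SMS messaging system". CO is not part of this definition.

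The month-6 text in section 8.6.3 opens with "Have you smoked a combustible cigarette since your last visit" and does not mention payment. Appendix 15 gives a maximum of 950 dollars and does not list the month-6 payment.

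**The concern.** Elsewhere the plan pays regardless of the answer. Daily texts earn the same whether the participant smoked or not, CO is taken from everyone at V1 to V7, and each visit is paid whatever the reading. Month 6 is the exception. A participant who texts that they are smoking has no described way to earn anything. One who texts that they are abstinent can earn 25 dollars by attending.

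Two mechanisms could raise the reported rate. Relapsed smokers may reply less often than abstainers, and some may report abstinence falsely. Section 13.1.1 names persistence of switching as the main goal of this follow-up. The denominator is limited to those abstinent in weeks 8-11, so a few people can move the estimate noticeably.

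**Working it through.** **1. The stated payment total.** Appendix 15 lists 25 dollars for V1, 75 dollars for each of V2 to V7, and 5 dollars a day for about 91-95 days.

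- At 95 days: 25 + 6 x 75 + 5 x 95 = 25 + 450 + 475 = 950 dollars, which reproduces the form.
- At 91 days: 25 + 450 + 455 = 930 dollars.
- With the month-6 payment from section 4.7 added: 955 dollars (91 days) to 975 dollars (95 days).

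The 950 dollars therefore omits the month-6 payment.

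**2. Who can be paid at month 6.**

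| Month-6 behaviour | Paid for the text (4.7) | Asked for CO (8.4) | Can earn 25 dollars |
|---|---|---|---|
| No reply | No | No | No |
| Texts that they are smoking | No | No | No |
| Texts that they are abstinent, does not attend | No | Yes | No |
| Texts that they are abstinent, gives a CO reading of any value | No | Yes | Yes |

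**3. Weight of one person.** As examples of the denominator, take the go thresholds of 16/25 and 28/50. One false claim adds 1/16 = 6.3 points or 1/28 = 3.6 points.

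**4. Differential reply.** The documents give no month-6 reply, misreport or relapse rates, so every input here is an assumption. Let t be true persistence, ra the abstainers' reply rate (90%) and rs the smokers' reply rate, with all replies truthful.

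- Responders only: t x ra / (t x ra + (1 - t) x rs)
- Non-response counted as smoking: t x ra

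| t | Responders only, rs = 90% | rs = 70% | rs = 50% | Non-response = smoking, any rs |
|---|---|---|---|---|
| 40% | 40% | 46.2% | 54.5% | 36% |
| 50% | 50% | 56.3% | 64.3% | 45% |
| 60% | 60% | 65.9% | 73.0% | 54% |
| 80% | 80% | 83.7% | 87.8% | 72% |

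For example, at t = 50% and rs = 70%: 0.45 / (0.45 + 0.35) = 56.3%. With rs at 50-70%, the responders-only excess over t runs from 83.7 - 80 = 3.7 points to 54.5 - 40 = 14.5 points. When non-response counts as smoking, the estimate lies below t in every row.

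**5. False claims.** Suppose everyone replies, self-report alone is scored, and a share f of smokers report abstinence. The reported rate is t + (1 - t) x f. At an assumed t of 60%:

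| f | Reported rate | Extra abstinent of 16 | Extra abstinent of 28 |
|---|---|---|---|
| 5% | 62% | 0.32 | 0.56 |
| 10% | 64% | 0.64 | 1.12 |
| 20% | 68% | 1.28 | 2.24 |
| 30% | 72% | 1.92 | 3.36 |

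If CO overrides the text, false claims by those who attend drop out and the excess falls toward zero.

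**6. Which scoring rule applies.** Section 13.1.1 defines switching at each time point by self-report confirmed by CO below 5 ppm, whereas section 2.2 rests the month-6 outcome on self-report. The same section counts participants lost to follow-up as not switched, in a sentence tied to the weeks 8-11 outcome. It is not expressly extended to month 6. Nothing says how a discordant or missing month-6 CO reading, or month-6 non-response, is scored. The documents therefore do not settle which column of step 4 applies, or whether the step 5 excess survives.

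**The case against.** A reader might infer that the plan pays for the endpoint answer itself. Section 4.7 does not support that. Texting abstinence earns nothing; the money is for coming in and giving a reading. A false claimant would have to take the test that section 8.4 collects for verification. The sum equals the V1 payment and is one third of a V2 to V7 payment. This stands: the answer opens access to the payment, and attendance earns it.

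A reader might also infer that the 6-month rate is biased upward. That does not follow either. It depends on the two scoring rules that the plan leaves open, and no passage plans a responders-only analysis. The lost-to-follow-up clause in section 13.1.1 carries no explicit time limit. If it reaches month 6, differential reply cannot raise the rate. If the CO criterion in that section governs, attending false claimants are removed.

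Finally, the incentive works only if participants know of the 25 dollars when they reply. The month-6 text and Appendix 15 do not mention it, and under section 8.4 the request to attend comes after the answer. The consent pages are not in the copy reviewed, so advance knowledge can be neither shown nor excluded.

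The asymmetry itself remains. The month-6 text is unpaid, and the only payment is closed to those who report smoking. Neither scoring rule gives relapsed smokers a reason to reply.

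**Conclusion.** The point holds as a minor design weakness. Sections 4.7 and 8.4 together make month-6 payment reachable only after a report of abstinence, while section 2.2 takes the outcome from that report. This creates a risk of upward bias if self-report alone is scored or only responders are analysed. It is not evidence that bias will occur.

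Its size cannot be computed from the documents. The responders-only excess of 3.7 to 14.5 points requires true persistence of 40-80%, 90% reply among abstainers and 50-70% among smokers, none of which the documents state. The false-claim excess of 2 to 12 points (62% - 60% to 72% - 60%) likewise rests on assumed misreporting of 5-30% at 60% persistence.

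The outcome is secondary. The go/no-go thresholds in sections 3.1.1 to 3.1.3 use switching at V7, so no stated decision changes.

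**What to change.** In section 4.7, add a fixed payment to every completer who answers the month-6 text, whatever they report. Keep the 25 dollars as compensation for the CO visit. Replacing it with travel cover could lower attendance and weaken verification. List both payments in Appendix 15 and correct its total: if the reply payment is 25 dollars, the 95-day maximum becomes 950 + 25 + 25 = 1,000 dollars. Align sections 2.2 and 8.4 with the change.

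Cost: at 25 dollars per reply, 25 x 25 = 625 dollars for 25 participants and 25 x 50 = 1,250 dollars for 50, plus a payment-form and consent update. A small asymmetry remains, because the CO visit is still offered only to those reporting abstinence. The payment change gives relapsed smokers a reason to reply under any scoring rule. It does not replace rules for discordant CO, missing CO and non-response at month 6, which are a separate gap.
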